Success Criteria for the Primary Effectiveness Endpoint – Non-Inferiority	If the P value from the Farrington-Manning standardized test is <0.025, the rate of the primary effectiveness endpoint for the Lotus Valve will be concluded to be non-inferior to the CoreValve rate. This corresponds to the one-sided upper 97.5% confidence bound on the difference between treatment groups (Lotus Valve minus CoreValve) for the observed rate of the primary effectiveness endpoint being less than delta.

REPRISE III: REpositionable Percutaneous Replacement of Stenotic Aortic Valve through Implantation of Lotus™ Valve System – Randomized Clinical Evaluation	
Statistical Test Method for the Primary Effectiveness Endpoint – Superiority	
A chi-square test will be used to test the two-sided hypothesis of superiority of the Lotus Valve versus CoreValve:
 $H_0: P_{E\_Lotus} = P_{E\_Control}$ $H_1: P_{E\_Lotus} \neq P_{E\_Control}$ 
where <math>P_{E\_Lotus}</math> and <math>P_{E\_Control}</math> correspond to the rates of the primary effectiveness endpoint for the Lotus Valve group (test) and the CoreValve group (control), respectively.
 
The primary analysis set for superiority test of the primary effectiveness endpoint is the ITT analysis set. This endpoint will also be analyzed for the as-treated and implanted analysis sets.

Sample Size Parameters for the Primary Effectiveness Endpoint – Superiority	
 
• Expected Lotus Valve (test) rate <math>P_{E\_Lotus} = 22\%</math>
 
• Expected CoreValve (control) rate <math>P_{E\_Control} = 32\%</math>
 
• Test significance level (<math>\alpha</math>) = 0.05 (2-sided)
 
• Test : Control ratio = 2:1
 
• Power (<math>1-\beta</math>) = 80%
 
• Total number of evaluable subjects = 684
 
• Expected rate of attrition = 10%
 
• Given enrollment of 912 subjects (608 Lotus Valve, 304 CoreValve) and 10% attrition, there is approximately 86% power to show superiority with the given expected rates
 

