### 4.1. *Justification for the Use of the Investigational Device in Human Subjects*

#### 4.1.1. Treatments for Aortic Stenosis

The incidence of aortic stenosis (AS), which most commonly occurs in the very elderly, is increasing due to the aging of the world-wide population and the lack of drug therapies to prevent, halt, or effectively slow the stenotic process. It is estimated that nearly 5% of elderly  $\geq 75$  years of age have AS and its prevalence is expected to increase as a result of an aging population. Aortic stenosis is associated with high rates of death and complications after the appearance of symptoms.

The standard of care for AS in patients who do not have serious comorbidities is surgical aortic valve replacement (SAVR), which has been shown to reduce symptoms and improve survival. Between 1999 and 2011, the rate of surgical AVR for elderly subjects in the United States has increased and outcomes have improved. However, up to one-third of patients with severe AS are not treated with SAVR because of their comorbidities and

consequent peri-operative risk (e.g., advanced age, left ventricular dysfunction, etc.). With standard medical therapy, mortality after 1 year among these patients may be as high as 50%. Percutaneous transluminal aortic valvuloplasty, which was introduced as an alternative to SAVR in elderly and/or high-surgical-risk subjects, can provide symptomatic relief and/or temporary improvement but does not provide definitive treatment in subjects with severe calcific AS. It is also associated with relatively high mortality and complication rates.

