## **8.2. Treatment Assignment**

Screening materials from eligible subjects who are identified by the investigators as having met the inclusion and exclusion criteria (see below Table 9.2-1 and Table 9.3-1, respectively) and who provide written informed consent, will be reviewed by a Case Review Committee (CRC; see Section 22.2) to assess and confirm suitability of subjects for enrollment.

For the randomized cohort, eligible subjects will be randomized in a 2:1 allocation to receive either the Lotus Valve System (test) or a commercially available self-expanding CoreValve® Transcatheter Aortic Valve Replacement System (control). The randomization schedules will be computer-generated, using a pseudo-random number generator. Randomization will be stratified by center and by high or extreme risk status (see Section 26.2 for definitions). All randomized subjects will have unique identification numbers. Random permuted blocks will be employed to ensure approximate balance of treatment allocation within each stratum. Instructions on randomization are provided in the Manual of Operations. Subject should be randomized within 7 calendar days of CRC approval. Subjects should be treated within 14 calendar days of randomization and no later than 30 calendar days after randomization.

**Note:** There will be a non-randomized roll-in phase with only the test device for centers that do not have previous experience implanting the Lotus Valve; each of these centers will perform at least 2 roll-in cases before commencing randomization. All roll-in subjects will have unique identification numbers. Subjects receiving the 21 mm Lotus Valve will be enrolled in a non-randomized, nested registry cohort to assess safety and effectiveness. After enrollment of the randomized cohort is completed, subjects will be enrolled in a U.S. Continued Access Study cohort with the Lotus Valve (23 mm, 25 mm, and 27 mm valve sizes) to further assess performance and safety. Additionally, subjects will be enrolled in a non-randomized, nested registry cohort with the 23 mm, 25 mm or 27 mm LOTUS Edge Valve (LOTUS Edge Nested Registry) to confirm performance of the Lotus Valve implantation procedure with the Edge delivery system. There will also be a non-randomized, roll-in phase with the 29 mm LOTUS Edge Valve for centers that do not have previous

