#### 12.1.1.3. Statistical Methods – Primary Safety Endpoint

All subjects who are enrolled and randomized will be eligible for evaluation. Any events or hospitalizations occurring after enrollment but prior to the index procedure should be entered in the electronic data capture system; events with onset date starting from the time of the index procedure will be included in the primary endpoint analysis.

Handling of dropouts and missing data will depend on their frequency and the nature of the outcome measure. Sensitivity analyses (e.g., tipping-point analysis) will be performed to assess the impact of subjects with inadequate follow-up (i.e., missing data) on the primary endpoint and to assess the robustness of the conclusion of the primary analysis. The sensitivity analysis of the primary endpoint, including events occurring after enrollment but prior to the index procedure, will be performed. Statistical models that account for censored data will be employed in appropriate circumstances (e.g., for time-to-event outcomes). Suspected invalid data will be queried and corrected in the database prior to statistical analysis. Additional information may be found in the Statistical Analysis Plan.

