#### 12.1.2.3. Statistical Methods – Primary Effectiveness Endpoint

Procedures similar to that described in Section 12.1.1.3 and discussed in the Statistical Analysis Plan will be applied to analysis of the primary effectiveness endpoint.

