### **12.2.4. Reporting Events**

For all subjects in the roll-in (with the 23 mm, 25 mm, or 27 mm Lotus Valve), Lotus 21 mm Nested Registry, LOTUS Edge Nested Registry, roll-in with the 29 mm LOTUS Edge Valve, LOTUS Edge 29 mm Nested Registry, and U.S. Continued Access Study cohorts, all events that occur from the start of the index procedure will be reported. For all randomized subjects, events from the time of randomization onward will be reported. For randomized subjects who do not have an attempted procedure, events from the date of randomization to 1 year post-randomization will be reported. For time based clinical events, the cut-off for events for 30-day endpoints will be 30 days, for 6-month endpoints will be 180 days, for 1-year endpoints will be 365 days, and for 2-5 year endpoints will be 365 days times the number of years. For events at discharge or 7 days post-procedure, the cut-off for events will be the earlier of the date of discharge or 7 days post-procedure for each subject.

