DEATH	
All-cause Death Death from any cause after a valve intervention.
 
Cardiovascular Death Any one of the following criteria is met.
 
 
• Any death due to proximate cardiac cause (e.g., myocardial infarction, cardiac tamponade, worsening heart failure)
 
• Sudden or unwitnessed death
 
• Death of unknown cause
 
• Death caused by noncoronary vascular conditions such as neurological events, pulmonary embolism, ruptured aortic aneurysm, dissecting aneurysm, or other vascular disease
 
• All procedure-related deaths, including those related to a complication of the procedure or treatment for a complication of the procedure
 
• All valve-related deaths including structural or nonstructural valve dysfunction or other valve-related adverse events
 
 
Non-cardiovascular Death
 
 
• Any death in which the primary cause of death is clearly related to another condition (e.g. trauma, cancer, suicide)
 

DEVICE DEFICIENCY Ref: ISO 14155:2011 Ref: MEDDEV 2.7/3 12/2010	
inadequacy of a medical device with respect to its identity, quality, durability, reliability, safety or performance.
 
Note 1: Device deficiencies include malfunctions, use errors, and inadequate labeling.

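### As written, the ITT superiority test of the 1-year effectiveness composite leaves out deaths and disabling strokes between randomization and the index procedure, and other sections of the plan conflict with that rule

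*Combined protocol and SAP*

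**What the plan says.** - **Event rule.** Section 12.1.1.3 (primary safety endpoint) asks that events after enrollment but before the procedure be entered in the data capture system, and then states that "events with onset date starting from the time of the index procedure will be included in the primary endpoint analysis". The same section opens by making all randomized subjects eligible for evaluation.
- **Carry-over to effectiveness.** Section 12.1.2.3: "Procedures similar to that described in Section 12.1.1.3 and discussed in the Statistical Analysis Plan will be applied to analysis of the primary effectiveness endpoint". It makes no exception for the ITT set.
- **Definition of death.** Table 26.2-1 defines all-cause death as "Death from any cause after a valve intervention".
- **Analysis set.** Synopsis: "The primary analysis set for superiority test of the primary effectiveness endpoint is the ITT analysis set". Section 12.2.1 repeats this, and section 10.1.2 places enrollment at randomization.
- **Waiting period.** Section 8.2: "Subjects should be treated within 14 calendar days of randomization and no later than 30 calendar days after randomization".
- **Text pointing the other way.** Section 12.2.4 reports events from randomization for all randomized subjects. For those with no attempted procedure, "events from the date of randomization to 1 year post-randomization will be reported". Note b of Table 11.1-1 dates follow-up from randomization where no implant is attempted.
- **Sensitivity analysis.** Section 12.1.1.3 adds that a sensitivity analysis of the primary endpoint, "including events occurring after enrollment but prior to the index procedure, will be performed".

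**The concern.** An ITT comparison should count what happens to every subject from randomization on. A subject who dies while waiting has had neither an index procedure nor a valve intervention, so that death fails both the event rule in 12.1.1.3 and the definition in Table 26.2-1. A subject who has a disabling stroke while waiting and is then treated fails the event rule for that stroke. Either way, the superiority test would condition its events on reaching the procedure, which is a post-randomization exclusion under an ITT label.

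This is the only ITT-primary test that contains mortality; the secondary endpoint is also ITT-primary but is regurgitation alone. For effectiveness the plan states no denominator rule, so a subject who dies waiting could be an event, a non-event or excluded. For the ITT run of the safety endpoint, 12.1.1.1 restricts the denominator to subjects with an event within 30 days after the procedure or at least 23 days of follow-up after it. A waiting death meets neither condition and leaves both numerator and denominator.

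**Working it through.** **1. Reproduce the plan's superiority figures.** Inputs from the synopsis and 12.1.2.2.2: 22% vs 32%, two-sided 0.05, 2:1, 10% attrition, 912 randomized.

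- Pooled rate = (0.32 + 2×0.22)/3 = 0.2533.
- Control n = [1.960·√(0.2533×0.7467×1.5) + 0.8416·√(0.32×0.68 + 0.22×0.78/2)]² / 0.10² = (1.0440 + 0.4636)²/0.01 = 227.3, rounded up to 228. Total 3×228 = **684**, as stated.
- Evaluable at 912: 0.9×912 = 820.8 (273.6 control, 547.2 Lotus). Power = Φ[(0.10 − 1.960×0.03220)/0.03330] = Φ(1.108) = **86.6%**; the plan says about 86%.

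So no error in sample size or power follows from this point.

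**2. Size of the affected group (assumptions, not document figures).** The documents give no death rate for the wait. Take a constant hazard and let every subject wait the full time w: r = 1 − (1 − m)^(w/365). For m, use two values:
- 11.6%: the 1-year all-cause mortality after implant in the REPRISE II full cohort (Table 4.1-4, 29/249);
- 32%: the whole expected control rate of the composite taken as death, as an upper assumption.

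To see the effect on power, add waiting deaths equally in both arms: each rate p becomes p + r(1 − p).

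| Annual mortality m | Wait w | r | Of 912 | Power |
|---|---|---|---|---|
| 11.6% | 14 days | 0.47% | 4.3 | 86.0% |
| 11.6% | 30 days | 1.01% | 9.2 | 85.3% |
| 32% | 14 days | 1.47% | 13.4 | 84.8% |
| 32% | 30 days | 3.12% | 28.5 | 82.6% |

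About 4 to 28 subjects, then, and a loss of 0.6 to 4.0 points of power. Disabling strokes during the wait are not in this count.

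**3. Can so few events matter?** Only near the boundary. With 140/547 Lotus and 88/274 CoreValve events, p = 0.049 (chi-square, no continuity correction).

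- One further Lotus death gives 0.054 if the subject is added to numerator and denominator, or 0.056 if a non-event becomes an event.
- One further CoreValve death gives 0.041 or 0.038.

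The shift can go either way, and it depends on the denominator rule that the plan leaves unstated.

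**The case against.** **The exclusion is not settled.** Section 12.1.1.3 is written for the safety endpoint, whose primary set is Implanted. It reaches effectiveness only through the word similar and a reference to a Statistical Analysis Plan, and no separate SAP text in the combined document resolves the matter. Section 12.2.4 and note b of Table 11.1-1 use randomization as the origin for the very subject who dies waiting. This stands to the extent that the documents conflict; a reader might infer a clean, deliberate removal of these deaths, and that is more than the text supports. But 12.2.4 governs reporting and note b governs visit dates. Neither says what enters the primary endpoint analysis, and 12.1.1.3 does.

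**The sensitivity analysis covers it.** It does include pre-procedure events, so they are not lost. A reader might infer from Table 26.2-1 that even this analysis would miss waiting deaths, but the wording of 12.1.1.3 points the other way. It still does not decide success; the superiority claim rests on the primary analysis.

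**The size could be read as much larger.** Section 4.1.1 says "mortality after 1 year among these patients may be as high as 50"%. Applied to a full 14- or 30-day wait for all 912, that gives about 24 or 51 deaths. The documents do not support that size here. The 50% is an upper figure for patients on medical therapy, the trial excludes subjects with life expectancy under 12 months, cardiogenic shock or need for emergency surgery, and section 8.2 gives a target and a limit, not a typical wait.

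**A bias toward Lotus could be inferred.** Sponsor personnel attend every Lotus implant (11.7.2.2) and inexperienced centers need six proctored cases (17.4.1), so one might suppose a longer Lotus wait. No document gives waiting time by arm, roll-in cases count toward the six and precede randomization, and the time limits in 8.2 apply to both arms.

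**Conclusion.** The concern holds as an inconsistency that affects the validity of the ITT superiority claim. On the literal text of 12.1.1.3, 12.1.2.3 and Table 26.2-1, deaths and disabling strokes between randomization and the index procedure are not events in that test. This contradicts the ITT label and sits in conflict with 12.2.4 and note b of Table 11.1-1.

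The estimate of about 4 to 28 of 912 rests on two assumptions: every subject waits the full 14 or 30 days, which overstates it, and annual mortality lies between 11.6% and 32%. The lower value is post-implant mortality and may be too low for untreated patients. On these figures power stays above 80%, no direction of bias is shown, and the stated sample size is unaffected. It should be corrected before analysis, because the success rule should not depend on an unstated choice about a handful of post-randomization deaths.

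**What to change.** - **Section 12.1.2.3.** State that in the ITT analysis of the effectiveness endpoint, including the superiority test, all deaths and disabling strokes from randomization count: through 365 days after the index procedure, or through 365 days after randomization where no procedure is attempted. State that subjects who die before a procedure stay in numerator and denominator. Closing at 365 days after the procedure keeps the clinical components aligned with the 12-month echocardiogram, which is scheduled from the procedure.
- **Implanted and As-Treated sets.** Keep the index-procedure clock.
- **Safety endpoint (12.1.1.1, 12.1.1.3).** Keep the 30-day post-procedure window. For the ITT run, add pre-procedure deaths and strokes to it, with those subjects in the denominator. Do not move the window to 30 days after randomization: section 8.2 allows treatment up to day 30, so procedural events could fall outside it.
- **Table 26.2-1.** For randomized subjects, define all-cause death as death from any cause after enrollment.

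The cost is wording only, since events are already reported from randomization (12.2.4 and 21.1). The small downside is that ITT event rates rise slightly.

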#### 12.1.2. Primary Effectiveness Endpoint

The primary effectiveness endpoint is the composite of all-cause mortality, disabling stroke, or moderate or severe paravalvular aortic regurgitation (based on independent core lab assessment) at 1 year.

##### 12.1.2.1. Statistical Hypothesis for the Primary Effectiveness Endpoint

###### 12.1.2.1.1 *Primary Hypothesis*

The primary statistical hypothesis is that the rate of the primary effectiveness endpoint (composite of all-cause mortality, disabling stroke, or moderate or severe paravalvular aortic regurgitation [based on independent core lab assessment] at 1 year) for the Lotus Valve group is non-inferior to that for the CoreValve group.

The null and alternative hypotheses for the primary hypothesis of the primary effectiveness endpoint are as follows:

$$H_0: P_{E\_Lotus} \text{ minus } P_{E\_Control} \geq \Delta \text{ (Inferior)}$$

$$H_1: P_{E\_Lotus} \text{ minus } P_{E\_Control} < \Delta \text{ (Non-inferior)}$$

where  $P_{E\_Lotus}$  and  $P_{E\_Control}$  correspond to the rates of the primary effectiveness endpoint for the Lotus Valve group (test) and the CoreValve group (control), respectively, and  $\Delta$  (delta) is the non-inferiority margin.

A Farrington-Manning test will be used to test the one-sided hypothesis of non-inferiority in the difference between the rates of the two treatment groups, as described in the Statistical Analysis Plan. If the  $P$  value from the Farrington-Manning standardized test is  $<0.025$ , the rate of the primary effectiveness endpoint for the Lotus Valve will be concluded to be non-inferior to the CoreValve rate. This corresponds to the one-sided upper 97.5% confidence bound on the difference between treatment groups (Lotus Valve minus CoreValve) for the observed rate of the primary effectiveness endpoint being less than the noninferiority margin.

#### 12.1.2.1.2 Secondary Hypothesis

The secondary statistical hypothesis is that the rate of the primary effectiveness endpoint (composite of all-cause mortality, disabling stroke, or moderate or severe paravalvular aortic regurgitation [based on independent core lab assessment] at 1 year) for the Lotus Valve group is superior to that for the CoreValve group. This test will be carried out only if the null hypothesis from the statistical hypothesis is rejected for the primary safety endpoint (Section 12.1.1), the primary hypothesis of the primary effectiveness endpoint (Section 12.1.2), and the secondary endpoint (Section 12.1.3), and the rate for the primary effectiveness endpoint for the Lotus group is less than that of the CoreValve group.

The null and alternative hypotheses for the secondary hypothesis of the primary effectiveness endpoint are as follows:

$$H_0: P_{E\_Lotus} = P_{E\_Control}$$

$$H_1: P_{E\_Lotus} \neq P_{E\_Control}$$

where  $P_{E\_Lotus}$  and  $P_{E\_Control}$  correspond to the rates of the primary effectiveness endpoint for the Lotus Valve group (test) and the CoreValve group (control), respectively.

A chi-square test will be used to test the two-sided hypothesis of superiority between the rates of the two treatment groups, as described in the Statistical Analysis Plan. If the  $P$  value from the chi-square test is  $<0.05$  and the rate of the Lotus Valve group is less than the rate of the CoreValve group, the rate of the primary effectiveness endpoint for the Lotus Valve will be concluded to be superior to the CoreValve rate. This corresponds to the two-sided upper 95% confidence bound on the difference between treatment groups (Lotus Valve minus CoreValve) for the observed rate of the primary effectiveness endpoint being less than zero.

#### 12.1.2.2. Sample Size Parameters for the Primary Effectiveness Endpoint

##### 12.1.2.2.1 Primary Hypothesis

The sample size calculation for the primary hypothesis of the primary effectiveness endpoint at 1 year is based on the following assumptions.

- Expected Lotus Valve (test) rate = 32%
- Expected CoreValve (control) rate = 32%

- Non-inferiority margin ( $\Delta$ ) = 9.5%
- Test significance level ( $\alpha$ ) = 0.025 (1-sided)
- Test : Control ratio = 2:1
- Power ( $1-\beta$ ) = 80%
- Total number of evaluable subjects = 819
- Expected rate of attrition = 10%

Given the above assumptions, at least 912 randomized subjects (608 Lotus Valve, 304 CoreValve) are needed to account for attrition.

#### *12.1.2.2.2 Secondary Hypothesis*

The sample size calculation for the secondary hypothesis of the primary effectiveness endpoint at 1 year is based on the following assumptions.

- Expected Lotus Valve (test) rate = 22%
- Expected CoreValve (control) rate = 32%
- Test significance level ( $\alpha$ ) = 0.05 (2-sided)
- Test : Control ratio = 2:1
- Expected rate of attrition = 10%

Given enrollment of 912 subjects (608 Lotus Valve, 304 CoreValve) and 10% attrition, there is approximately 86% power to show superiority with the given expected rates.

#### 12.1.2.3. Statistical Methods – Primary Effectiveness Endpoint

Procedures similar to that described in Section 12.1.1.3 and discussed in the Statistical Analysis Plan will be applied to analysis of the primary effectiveness endpoint.

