**Table 11.1-1: Study Event Schedule**

Assessment	Screening a	Baseline	Procedure	Within 1 Day Post-procedure	Prior to Discharge or 7 Days Post-Procedure	30 Days b (±7 Days) Office Visit	6 Months b (±30 Days) Office Visit	12 Months b (±30 Days) Office Visit	24–60 Months b [Annual] (±45 Days) Office Visit
CT angiogram of iliofemoral system m	X								
Annual imaging (rotational X-ray) n								X	X
QOL surveys o		X				X	X	X	X p
Procedural cine-angiography (including post-deployment aortogram) q			X						
Pacemaker interrogation r						X		X	
AE and ADE assessments s			X	X	X	X	X	X	
Device deficiencies, SAE, SADE, USADE, UADE and CEC event assessments t			X	X	X	X	X	X	X
4D CT imaging of prosthetic valve u						X		X	

- a: It is recommended that screening materials for CRC review be submitted electronically within 5 days of a scheduled CRC call in order to be considered for review (unless otherwise specified).
- b: All follow-up dates will be calculated from the date of the (attempted) index procedure (or randomization in randomized subjects where no implant is attempted). Visits must be an office/clinical visit, but may be done in-hospital should the subject be admitted at the time. Subjects who are enrolled but do not receive a study device (test or control) will be followed for 1 year to assess for safety but do not need to have protocol required TTE or ECG.
- c: Study-specific consent includes screening consent to perform required assessments that will be evaluated by the CRC to confirm subject eligibility. If the study Informed Consent Form is modified during the course of the study, study subjects will be re-consented as necessary.

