#### 11.10. *Follow-up*

All implanted subjects will be evaluated at 30 days, 6 months, 12 months, 24 months, 36 months, 48 months, and 60 months post index procedure. Subjects who do not have a study device implanted will be assessed through 1 year post procedure for safety/adverse events. Physical clinic visits or follow-up visits are scheduled for appointed times after the date of the procedure. It is important that this schedule be maintained as closely as possible for all subjects. Boston Scientific Corporation recognizes that subjects may not be able to return for all scheduled visits at precisely the date required, and therefore, a period of time in which each visit is allowed is indicated in Table 11.1-1. Visits not completed will be considered missed and recorded as protocol deviations. Visits completed outside these windows will be recorded as protocol deviations. After 6 months, visits will be scheduled on an annual basis from 1 through 5 years. Each follow-up visit must be performed by study personnel; data from the required tests and images as well as medical assessments will be recorded in source documentation and captured in the eCRFs. The determination of specified study endpoints and measurements such as valve function and CEC events will require data from images and tests as outlined in the event definitions (Table 26.2-1).

In the event that study personnel learn of a subject's hospitalization outside the study center, the center should make every effort to obtain copies of reports or results based on tests (e.g., echocardiogram) and/or procedures performed on the study subject.

**Note:** A subject who has received a study valve should not be enrolled in a clinical trial of an investigational drug/device/treatment until the subject has reached the REPRISE III primary effectiveness endpoint (1 year).

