#### 11.10.2. 6-Month (180±30 Days) Follow-up

All implanted subjects must be evaluated at 6 months after the index procedure. During the 6-month follow-up, the following assessments must be completed. The REPRISE III eCRFs identify the specific data points to be collected.

- Weight and height
- NYHA classification
- Modified Rankin Scale score, which must be performed by a neurology professional or certified personnel (external or internal certification); assessors should be independent (not involved with the care of study subjects).
- 12-lead ECG per the Core Laboratory guidelines (see study Manual of Operations) and must be forwarded for analysis
- Current antiplatelet, anticoagulant (if applicable) medications
- TTE, including assessment of effective orifice area, peak systolic and mean aortic valve gradient pressure, aortic regurgitation assessment, mitral regurgitation, LVEF, left ventricular end-diastolic and end-systolic diameter, TR jet velocity and LA volume, per the Echocardiography Core Laboratory procedure guidelines (see study Manual of Operations). It must be sent to the Core Laboratory for independent analysis.  
**Note:** TTE must be done for all subjects who have a valve implanted in the aortic position during the index procedure. Subjects who do not receive a transcatheter valve during the index procedure are not required to have follow-up TTE.
- Complete adverse event (AE, SAE, SADE, UADE/USADE, ADE and CEC events) and device deficiencies assessment (with associated treatment)
- Quality of Life Surveys: Kansas City Cardiomyopathy and SF-12 Quality of Life Questionnaires

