#### 12.1.1.1. Statistical Hypothesis for the Primary Safety Endpoint

The statistical hypothesis is that the rate of the primary safety endpoint (composite of all-cause mortality, stroke, life-threatening and major bleeding events, stage 2 or 3 acute kidney injury, or major vascular complications at 30 days) for the Lotus Valve is non-inferior to that for CoreValve.

The primary safety endpoint is expressed as the proportion of subjects who experience mortality, stroke, life-threatening and major bleeding events, stage 2 or 3 acute kidney injury, or major vascular complications within 30 days after the index procedure among all subjects who either experience mortality/stroke/life-threatening or major bleeding events/stage 2 or 3 acute kidney injury/major vascular complications within 30 days after the index procedure or are followed for at least 23 days after the index procedure.

The null and alternative hypotheses for the primary safety endpoint are as follows:

$$H_0: P_{S\_Lotus} \text{ minus } P_{S\_Control} \geq \Delta \text{ (Inferior)}$$

$$H_1: P_{S\_Lotus} \text{ minus } P_{S\_Control} < \Delta \text{ (Non-inferior)}$$

where  $P_{S\_Lotus}$  and  $P_{S\_Control}$  are the rates of the primary safety endpoint at 30 days for the Lotus Valve (test) group and the CoreValve group (control), respectively, and  $\Delta$  (delta) is the non-inferiority margin.

A Farrington-Manning standardized test will be used to test the one-sided hypothesis of noninferiority in the difference between the rates of the two treatment groups, as described in the Statistical Analysis Plan. If the  $P$  value from the Farrington-Manning standardized test is  $<0.025$ , the rate of the primary safety endpoint for the Lotus Valve will be concluded to be non-inferior to the CoreValve rate. This corresponds to the one-sided upper 97.5% confidence bound on the difference between treatment groups (Lotus Valve minus CoreValve) for the observed rate of the primary safety endpoint at 1 year being less than the non-inferiority margin.

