#### 12.1.3.3. Statistical Methods – Secondary Endpoint

Procedures similar to that described in Section 12.1.1.3 and discussed in the Statistical Analysis Plan will be applied to analysis of the secondary endpoint.

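### Does the missing rule for event-free survivors without a 1-year core-lab PVR grade undermine the primary effectiveness analysis?

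*Combined protocol and SAP*

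**What the plan says.** Section 12.1.1.1 defines who counts for the safety endpoint: subjects with an event within 30 days "or are followed for at least 23 days after the index procedure". Sections 12.1.2 and 12.1.3 give the composite and PVR their hypotheses, tests and sample sizes but no matching sentence. For methods, Section 12.1.2.3 refers to Section 12.1.1.3 and to procedures "discussed in the Statistical Analysis Plan will be applied to analysis of the primary effectiveness endpoint". Section 12.1.3.3 uses the same device: similar procedures "will be applied to analysis of the secondary endpoint". Section 12.1.1.3 reads: "Handling of dropouts and missing data will depend on their frequency and the nature of the outcome measure". It then commits to sensitivity analyses, naming tipping-point as an example.

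On timing, Section 12.2.4 fixes the clinical-event cut-off: "for 1-year endpoints will be 365 days". Section 11.10.3 and Table 11.1-1 place the 12-month visit, with its required core-lab echo, at 365±30 days. On late or early visits Section 11.10 adds: "Visits completed outside these windows will be recorded as protocol deviations".

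Section 12.2.1 makes the implanted set primary for non-inferiority and the ITT set primary for the superiority test and the PVR endpoint. In Table 11.1-1, footnote b says subjects without a study device "do not need to have protocol required TTE or ECG", while footnote i asks for echo in anyone with a valve in the aortic position.

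**The concern.** The composite mixes two kinds of component. Death and disabling stroke classify a subject whether or not an echo exists. A survivor without disabling stroke needs a core-lab PVR grade. The natural analogue of the safety rule, an event or a graded echo, would keep every death and stroke but lose event-free survivors. Observed rates would rise, and unequal echo completeness between arms would appear as a treatment difference. Wording that lets the handling depend on how much is missing also seems to leave the choice open until the missingness is known.

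Two smaller points are unsettled: whether an echo outside 365±30 days counts, and how ITT subjects without a prosthesis are classified. At stake are the non-inferiority result against a 9.5-point margin, the superiority test and the PVR test.

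**Working it through.** **1. The plan's own figure.** Inputs (Section 12.1.2.2.1): 32% in both arms, margin 9.5 points, one-sided 0.025, 2:1, 80% power, 10% attrition. For Farrington-Manning, the restricted estimates at a 9.5-point difference are 0.355 and 0.260.

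- s0 = √(0.355×0.645/2 + 0.260×0.740) = 0.554
- s1 = √(0.32×0.68×1.5) = 0.571
- Control n = [(1.960×0.554 + 0.842×0.571)/0.095]² = 272.1, rounded up to 273; total 3×273 = 819
- 819/0.9 = 910, raised to 912 for 2:1

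The stated 819 and 912 reproduce; power at 819 is 80.1%.

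**2. Missingness in REPRISE II** (Tables 4.1-3 and 4.1-4, 1 year).

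- Main cohort: 120 − 13 deaths = 107 survivors, 88 graded; 19/107 = 17.8% ungraded
- Full cohort: 249 − 29 = 220 survivors, 163 graded; 57/220 = 25.9%
- Removing the 4 and 9 disabling strokes as well, taken as alive and ungraded: 15/103 = 14.6% and 48/211 = 22.7%

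**3. Composite if ungraded event-free survivors are dropped.** The split of the 32% is not stated. I assume PVR rates r of 1.1% (Lotus) and 5.3% (CoreValve), from Section 12.1.3.2, among subjects free of death and stroke. The death-or-stroke share is D = (0.32 − r)/(1 − r), which gives 0.312 and 0.282. With missing fraction m unrelated to PVR:

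rate = [D + (1−D)(1−m)r] / [D + (1−D)(1−m)]

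Example, Lotus at m = 25.9%: (0.3124 + 0.5094×0.011)/(0.3124 + 0.5094) = 0.3180/0.8218 = 38.7%.

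| m, both arms | Lotus | CoreValve | Difference (points) | Retained of 912 |
|---|---|---|---|---|
| 14.6% | 35.4% | 35.1% | +0.3 | 819 |
| 17.8% | 36.3% | 35.9% | +0.4 | 799 |
| 22.7% | 37.7% | 37.2% | +0.5 | 767 |
| 25.9% | 38.7% | 38.1% | +0.6 | 747 |

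**4. Composite if everyone is kept and ungraded survivors count as PVR-free.** The undercount is (1−D)·m·r: 0.1-0.2 points for Lotus and 0.6-1.0 for CoreValve. The difference moves by 0.4-0.8 points, again against Lotus.

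**5. Unequal completeness under dropping.** With 20% missing in both arms the difference is +0.45. With 20% Lotus and 25% CoreValve it is −0.92; reversed, +1.94. An assumed 5-point imbalance therefore moves the difference by about 1.4-1.5 points, or 14-16% of the margin.

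**6. Power under dropping.** Power = Φ{[(0.095 − difference)√n_C − 1.960·s0]/s1}, with n_C one third of those retained. From 819 down to 747 retained:

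- both arms at 32%: 80.1% to 76.5%
- both arms at the inflated average: 78.0% to 72.4%
- arm-specific rates from step 3: about 75% to 67%
- all 912 kept, 32%: 84.1%

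**The case for a change.** The strongest case for a change is that the rule is absent from the protocol, the arithmetic is right, and one sentence would supply it. A tipping-point analysis tests a primary result but does not define one. Under the least favourable REPRISE II missingness, a complete-case rule could cost several points of power. Balance between arms cannot be known in advance. The ITT question is separate: PVR is leakage around a prosthesis, so a subject without one has no defined PVR status. Footnotes b and i do conflict for a subject given a non-study aortic valve.

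The absence stands as a statement about the protocol text, and so does the footnote conflict. Much of the rest weakens on inspection.

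- The 35-39% is an absolute rate under a denominator the protocol does not choose, while the test is on the difference.
- The documents do not say whether the planned 32% refers to all subjects or to evaluable ones. If evaluable, there is no inflation relative to the plan.
- REPRISE II is single-arm and cannot show imbalance. Part of its gap is image gradability: 163 PVR grades against 176 gradients.
- Echo is required for implanted subjects in both arms, and the implanted set is primary for non-inferiority. Subjects without a study device are outside it.
- The 1-year echo has a stated visit window; only the use of out-of-window echoes is unsettled.
- Section 12.3.5 requires changes made before analysis to be in an approved amended SAP, which limits late choice.

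**Conclusion.** No change to the plan follows. This is an unwritten detail, deferred to an SAP that is not in the text available here, and no figure in the plan is shown to be wrong. An analyst would fill it sensibly: death and disabling stroke count as events whatever the echo status; the grade from the 12-month visit is used; a subject with no prosthesis is classified on death and stroke; and the promised sensitivity analyses cover ungraded survivors. Earlier core-lab echoes exist to support this; of the 6-month echo, Section 11.10.2 says: "It must be sent to the Core Laboratory for independent analysis".

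The two obvious fills, dropping ungraded survivors or counting them PVR-free, move the tested difference by 0.3-0.6 and 0.4-0.8 points. Both shifts are against Lotus and small beside 9.5 points. Prescribing multiple imputation for PVR would be a debatable preference with little gain, because ungraded PVR can change a composite rate by at most about 1 point. At 14.6% missing, the retained number is the planned 819, so loss of that size is already budgeted.

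The conclusion rests on similar completeness in the two arms, missingness unrelated to PVR, and the split of the 32% inferred from the secondary-endpoint rates. If both arms had the same split, equal completeness would leave the difference unchanged. A marked imbalance would matter more, but none is shown. The clash between footnotes b and i is a clerical inconsistency in the visit schedule that has to be reconciled. It concerns only subjects given a non-study valve, and no result is shown to depend on it.
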